## 10.2 Notes Severity / Grading of Adverse Events

The assignment of the severity/grading should be made by the investigator responsible for the care of the participant using the definitions below.

Regardless of the classification of an AE as serious or not, its severity must be assessed according to medical criteria alone using the following categories:

**Mild:** does not interfere with routine activities

**Moderate:** interferes with routine activities

**Severe:** impossible to perform routine activities

A distinction is drawn between serious and severe AEs. Severity is a measure of intensity (see above) whereas seriousness is defined using the criteria in section 10.1, hence, a severe AE need not necessarily be a Serious Adverse Event.

## 10.3 Relationship to Trial Intervention

The assignment of the causality should be made by the investigator responsible for the care of the participant using the definitions in Table 4.

If any doubt about the causality exists the local investigator should inform the study coordination centre who will notify the Chief Investigator. In the case of discrepant views on causality between the investigator and others, the MHRA will be informed of both points of view.

**Table 4: Definitions of Causality**

Relationship	Description
Unrelated	There is no evidence of any causal relationship. N.B. Not reportable for this trial unless the event is death which should be reported on the death form within 7 days
Unlikely	There is little evidence to suggest there is a causal relationship (e.g. the event did not occur within a reasonable time after administration of the trial medication/intervention procedure). There is another reasonable explanation for the event (e.g. the participant's clinical condition, other concomitant treatment).
Possibly	There is some evidence to suggest a causal relationship (e.g. because the event occurs within a reasonable time after administration of the trial medication/intervention procedure). However, the influence of other factors may have contributed to the event (e.g. the participant's clinical condition, other concomitant treatments).
Probably	There is evidence to suggest a causal relationship and the influence of other factors is unlikely.

Almost certainly	There is clear evidence to suggest a causal relationship and other possible contributing factors can be ruled out.
-------------------------	--

An AE whose causal relationship to the intervention is assessed by the investigator as “possible”, “probable”, or “almost certain” is a related Adverse Event or related Adverse Reaction and should be reported to the CTRC (see Figure 1).

For TFESI patients:

When reporting the assignment of causality the investigator should make it clear if the AE is related to the IMP (steroid or local anaesthetic) or to the procedure i.e., the act of injecting.

### 10.4 Expectedness

It is not a regulatory requirement for reporting physicians to provide their opinion of expectedness; if any adverse events occur the Principal Investigator or delegated other should make an assessment of relatedness to the trial intervention and follow the correct reporting procedure (see section 10.6). The Chief Investigator (or agreed delegate) will undertake the assessment of expectedness.

For TFESI patients:

All events judged to be possibly, probably, or almost certainly related to the steroid and/or anaesthetic used during the TFESI, graded as serious and **unexpected** (see section 10.1 and Table 5 for list of Expected Adverse Events) will be reported as a **Suspected Unexpected Serious Adverse Reaction (SUSAR)** by the CTRC.

For TFESI / microdiscectomy patients:

All events judged to be possibly, probably, or almost certainly related to the microdiscectomy or TFESI *procedure (i.e. the act of injecting)*, graded as serious and **unexpected** (see Section 10.1 and Tables 5 and 6 for list of Expected Adverse Events) will be reported as a **related unexpected serious adverse event (RUSAE)** by the CTRC.

Based on available safety information for the trial interventions all the events listed in Table 5 and Table 6 are expected within the trial population and will not be subject to expedited reporting to the MHRA or REC. The Chief Investigator will also refer to Reference Safety Information (RSI) for a list of AEs associated specifically with the representative pharmaceutical agents used in the trial (see Section 7.2). The RSI is described within specific sections of Summary of Product Characteristics (SPCs) approved by the MHRA.

N.B. Tables 5 and 6 do not represent an exhaustive list and every related adverse event will be reviewed by the Chief Investigator against available relevant safety information to make an assessment of expectedness.

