The transforaminal mode (TFESI) of administration of the drug mixture into the epidural space, under fluoroscopic guidance, is reported to be the most successful in a prospective randomised study (compared to injection of saline or local anaesthetic in epidural space or intramuscular steroid or saline injection) and this is the route which will be considered in this study (11, 12). Relief of pain was corroborated by significant improvements in function and disability, and reductions in use of other health care.

TFESI is believed to be superior in efficacy to inter-laminar administration of ESI due to delivery of the drug closer and accurately to the site of the pathology/disc prolapse. A prospective study of TFESI ((5), n=48) for acute sciatica suggests long-term pain reduction in over 80% of patients. One recent RCT as mentioned above ((11); n=150) compared the outcomes of selective nerve root injection (SNRI) and local anaesthetic, local anaesthetic alone, or normal saline, and intramuscular injection of steroid or normal saline. The only radiological feature associated with successful outcome was the grade of nerve root compression. Of patients with low-grade root compression (n=71), 75% responded favourably to SNRI and avoided surgery by 12 months follow up.

Although little data exists directly comparing TFESI to inter-laminar steroid injections for sciatica, there are a number of on-going studies throughout the world at the recruitment stage specifically looking at this but are experiencing recruitment difficulties because of the lack of a surgical treatment arm. One recent study ((13); n=238) reported 65% of injections were effective at follow-up greater than 6 months (based on patient reported measures) suggesting that the administration of drug closer to the disc prolapse may improve efficacy when compared to other methods of administration.

Adverse events associated with SNRI procedures are rare, typically less than 1%, but can be severe and include paraplegia, infection, haematoma, intravascular injection of medication, direct nerve trauma, subdural injection of medication, air embolism, disc entry, urinary retention, radiation exposure, and hypersensitivity reactions.

The advantages of spinal injections are:

- a) They are a relatively cheap and low risk procedure compared to surgery.

- b) Success rates have been estimated to be as high as 75%.

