#### Previous studies of microdiscectomy for sciatica

Recent data from Peul et al (3, 6) suggests that surgical microdiscectomy may effectively relieve sciatica in 90% of patients with acute sciatica. This is comparable to favourable outcomes from conservative management of the condition at 12 months follow up. This above finding would suggest that there is a period of spontaneous resolution for this condition within the first 12 months of symptom onset, though surgical intervention could lead to quicker recovery. Treatment may be needed for patients in the acute phase of their condition and to prevent their symptoms from becoming chronic and resistant to treatment/intervention.

Surgery to remove a prolapsed lumbar intervertebral disc (PID) is regarded as the gold-standard treatment for acute sciatica. Adverse events are reported in up to 3% of operations and include the same spectrum of complications as SNRI but also death, paraplegia, sexual/bladder dysfunction and spinal fluid leak. Approximately 6% of operated herniated discs can recur and require re-operation (14). The long-term deleterious effects of this operation upon the patient are unknown. Specialist centres in the UK can carry out more than 500 primary microdiscectomy operations per year for this condition. The average length of stay for this procedure is two nights in hospital.

The advantages of microdiscectomy are:

- a) It has the highest reported success rate, working in 9 out of 10 patients.

Disadvantages are:

- a) It is expensive, requiring hospital admission.
- b) There are resource implications given that the skill level required to perform the procedure is high, requiring a consultant spinal surgeon (orthopaedic or neurosurgical surgeon) or their equivalent.
- c) It carries the highest level of morbidity/risk of all treatments.
- d) The long term consequences of surgical microdiscectomy are largely unknown.

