#### **Unexpected Adverse Reaction (UAR)**

An adverse reaction the nature and severity of which is not consistent with the information about the medicinal product in question set out in:

- In the case of a product with a marketing authorization, in the Summary of Product Characteristics (SPC) for that product.
- In the case of any other investigational medicinal product, in the investigator's brochure relating to the trial in question.

In the case of the NERVES trial this definition includes any adverse reaction the nature and severity of which is not consistent with that expected for the act of injection in the TFESI arm or surgical microdiscectomy and will be referred to as a Related Unexpected Serious Adverse Event (RUSAE). See Section 10.4 for more information.

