**Table 5: Expected Adverse Events associated with TFESI**

A: Events associated with TFESI procedure i.e., act of injecting
Soft tissue infection
Pulmonary Embolism
Deep Vein Thrombosis
Significant post procedural headache (low pressure headache)

Increased sciatic pain post injection          Neurological deficit including bladder/bowel issues          Anaphylaxis          Cauda equina syndrome          Foot drop          Discitis

B: Events associated with TFESI drugs (IMPs)
 
Adverse reaction related to administration of steroid (refer to relevant Reference Safety Information)          Adverse reaction related to administration of anaesthetic (refer to relevant Reference Safety Information)          Anaphylaxis

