The PIs at all institutions participating in the trial will be notified of any SUSARs or unexpected SAEs.

Patient safety incidents that take place in the course of research should be reported to the National Patient Safety Agency (NPSA) by each participating NHS Trust in accordance with local reporting procedures.

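### Protocol section 10.4 exempts every listed event from expedited reporting whatever its severity, against the test in 10.1, and lists neurological deficit for TFESI only

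*Protocol*

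**What the plan says.** Protocol section 10.1, under Unexpected Adverse Reaction, sets the general test: "An adverse reaction the nature and severity of which is not consistent with" the product information. It carries the same test over to the trial procedures, covering "any adverse reaction the nature and severity of which is not consistent with that expected for the act of injection in the TFESI arm" and likewise for microdiscectomy.

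Section 10.4 then defines two expedited classes. A serious, unexpected event related to the injected drugs is a SUSAR. A serious, unexpected event related to the act of injecting or to the operation is a RUSAE. For the RUSAE class it directs the reader to two places at once: "see Section 10.1 and Tables 5 and 6 for list of Expected Adverse Events". On expedited reports to the regulator and the ethics committee, it then says that "all the events listed in Table 5 and Table 6 are expected within the trial population and will not be subject to expedited reporting". A closing note says that the tables are not exhaustive and that the Chief Investigator will assess every related event for expectedness.

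Table 5A (the injection procedure) includes "Neurological deficit including bladder/bowel issues". Table 6A (the operation) has no such entry. Section 2.2 says that adverse events of nerve root injection are rare "but can be severe and include paraplegia", and that those of surgery "include the same spectrum of complications as SNRI but also death, paraplegia, sexual/bladder dysfunction and spinal fluid leak".

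On who is told, section 10.8 says "The PIs at all institutions participating in the trial will be notified of any SUSARs or unexpected SAEs". Section 10.8.1 promises investigators word of all SUSARs and RUSAEs.

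**The concern.** Expectedness is the switch that decides who hears of a serious related event and how soon. The protocol sets that switch in two ways. Section 10.1 looks at nature and severity; the exemption in 10.4 looks only at whether the event's name is on a list. The two give different answers for an event whose name is listed but whose severity is out of the ordinary, and these are the cases in which prompt reporting matters most.

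The second issue is comparability between arms. If a broad neurological term makes an injury expected after injection, and no matching term exists for surgery, one injury may follow two reporting routes depending on allocation. The REC and the other sites would then see an uneven picture of harm while the trial is running.

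**Working it through.** No arithmetic applies. The check sets the sections side by side and traces an event through them.

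**Step 1: the two tests.** Section 10.1 asks whether nature and severity are consistent with what is expected. The exemption sentence in 10.4 carries no condition. Tables 5A and 6A do not supply one: apart from the word significant before headache, the entries have no severity, outcome or fatality limit. A listed event of unusual severity is therefore open to being unexpected under 10.1 and is exempt under 10.4.

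**Step 2: what follows if 10.4 is applied as written.**

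| Classification | Expedited report | Notice to investigators |
|---|---|---|
| Drug-related, serious, unexpected (SUSAR) | MHRA and REC, 7 days if fatal or life-threatening, otherwise 15 | Yes (10.8, 10.8.1) |
| Procedure-related, serious, unexpected (RUSAE) | REC only, 15 days | Yes (10.8.1) |
| Serious, related, expected | None required | Not triggered by 10.8 or 10.8.1 |

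An event in the last row still reaches the CTRC within 24 hours (10.6) and appears in periodic lists (10.8, 10.8.2). Tables 5A and 6A concern procedures, so for their entries the loss is the 15-day REC report and the notice to investigators. The MHRA would not receive a RUSAE in any case.

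**Step 3: the tables line by line.** Each of Tables 5A and 6A has 10 entries.
- In both (8): soft tissue infection, pulmonary embolism, deep vein thrombosis, headache, anaphylaxis, cauda equina syndrome, foot drop, discitis.
- TFESI only (2): increased sciatic pain, neurological deficit.
- Microdiscectomy only (2): CSF leak, recurrent disc prolapse.

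The count closes: 8 + 2 = 10 for each table.

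**Step 4: what the lists show.** Embolism and anaphylaxis are in both tables, so they illustrate the severity conflict in both arms and say nothing about a difference between arms. The difference lies in the neurological entry. Paraplegia is named in section 2.2 for both procedures and in neither table. After injection it could be read into the broad entry in Table 5A. After surgery the nearest entries are cauda equina syndrome and foot drop, both narrower. The same injury could therefore be classed as expected in one arm and as a RUSAE in the other.

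**The case against.** The strongest reply is that 10.4 should not be read alone. It refers back to 10.1, and its closing note has the Chief Investigator assess every related event, which includes listed ones. Section 10.8 repeats that all serious events received are evaluated for expectedness. On that reading a listed event can be found unexpected on severity. This stands as a possible reading, and it means that a missed report is not a certain outcome. It does not remove the conflict. The note is attached to a statement that the lists are incomplete and does not say that severity can take a listed event out of the exemption. An assessor who did so would be acting against an unconditional sentence.

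There are also other routes. Section 10.8 recommends expediting a clinically important rate increase or qualitative change in an expected serious reaction, and a serious event linked to trial procedures that could change the conduct of the trial. Section 10.8.2 has all sites told if safety reports reveal implications for participants. Section 10.8.3 requires notice within 3 days of an urgent safety measure, and the IDSMC reviews safety at least annually (9.5.2). These are real safeguards. They rest on a recommendation, on a judgement, on a measure having been taken or on a meeting date, so they do not replace the routine trigger.

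On the arms, Table 6 is expressly not exhaustive, and section 2.2 names paraplegia for surgery, so the Chief Investigator might class it as expected there too. That also stands: a difference between arms is possible and is not fixed by the text.

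**Conclusion.** The point holds as an internal conflict, with an unexplained difference between the tables. Followed literally, 10.4 would deny a listed event of unexpected severity, in either arm, the expedited report and the investigator notice that 10.1 would give it. For procedure-related events that means losing the 15-day REC report, with periodic listing and partly discretionary routes left.

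A reader might infer more, and the documents do not support it:
- That paraplegia or a fatal embolism after injection is bound to go unreported. This ignores the link to 10.1 and the Chief Investigator's review, and paraplegia is listed by name nowhere.
- That the embolism gap is specific to injection. It is in both tables.
- That a 7-day deadline is lost. That limit is for drug-related SUSARs; procedure-related events fall under the 15-day REC rule.
- That the size is 74 x 0.01 = 0.74 events. The under-1% figure in section 2.2 covers all adverse events of nerve root injection, and section 7.2 allows repeat injections, so it says nothing about rare severe cases.

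The conclusion rests on the text of sections 10.1 to 10.8.3. The reporting flow chart (Figure 1) and the Reference Safety Information were not available for checking. The efficacy analysis is unaffected, and SAP section 20.2 tabulates reported events without regard to expectedness.

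**What to change.** 1. Reword the exemption in 10.4 so that a listed event is excused from expedited reporting only when its nature and severity are consistent with the tables and the Reference Safety Information, as 10.1 requires.
2. State there that the Chief Investigator's review may class a listed event as unexpected on severity.
3. Reconcile the neurological entry across Tables 5A and 6A, or give the reason for the difference. Which events count as expected is for the sponsor and the Chief Investigator to decide.
4. Check that Figure 1 agrees with the revised text.

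A rule that every fatal, life-threatening or permanently disabling listed event is unexpected should not be adopted. It would swap the expectedness test for a seriousness test, and section 10.2 keeps severity and seriousness apart.

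The cost is a few words in 10.4 and the two tables, no new data, and an occasional extra expedited report.

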**Table 5: Expected Adverse Events associated with TFESI**

A: Events associated with TFESI procedure i.e., act of injecting
Soft tissue infection
Pulmonary Embolism
Deep Vein Thrombosis
Significant post procedural headache (low pressure headache)

Increased sciatic pain post injection          Neurological deficit including bladder/bowel issues          Anaphylaxis          Cauda equina syndrome          Foot drop          Discitis

B: Events associated with TFESI drugs (IMPs)
 
Adverse reaction related to administration of steroid (refer to relevant Reference Safety Information)          Adverse reaction related to administration of anaesthetic (refer to relevant Reference Safety Information)          Anaphylaxis

**Table 6: Expected Adverse Events associated with microdiscectomy**

A: Events associated with microdiscectomy procedure
 
CSF leak          Significant post procedural headache (low pressure headache)          Soft tissue infection          Pulmonary Embolism          Deep Vein Thrombosis          Cauda equina syndrome          Foot drop          Discitis          Reoccurring disc prolapse          Anaphylaxis

B: Events associated with general anaesthetic (not required for reporting)
 
Throat pain/hoarseness          Injury to the mouth or teeth from the breathing tube          Drowsiness, confusion or restlessness          Nausea and/or vomiting          Breathing problems          Chest infection          Anaphylaxis

### 10.5 Follow-up After Adverse Events

All adverse events should be followed until satisfactory resolution or until the investigator responsible for the care of the participant deems the event to be chronic or the patient to be stable.

When reporting SAEs, RUSAEs and SUSARs the investigator responsible for the care of the participant should apply the following criteria to provide information relating to event outcomes: resolved; resolved with sequelae (specifying with additional narrative); not resolved/ongoing; ongoing at final follow-up; fatal or unknown.

### 10.6 Reporting Procedures

Any AE with causal relationship to either trial intervention assessed as possible, probable or almost certainly related should be reported to the CTRC using the trial specific adverse event CRF throughout the trial follow up period.

The PI or designated other should grade the event as '**not serious**' or '**serious**'.

- **Events graded as not serious**

If the event is graded as **not serious**, the adverse event CRF should be returned to the CTRC within 7 days of the clinical research team becoming aware of the event.

- **Events graded as serious**

If the event is graded as **serious** (see Section 10.1), the investigator should also complete the **Serious Adverse Event CRF and return to the CTRC within 24 hours** of the clinical research team becoming aware of the event and should contain the minimum information required for reporting (see Section 10.7). Any serious adverse event should also be reported as per local reporting procedures.

### **Include**

- An exacerbation of a pre-existing illness.
- An increase in frequency or intensity of a pre-existing episodic event/condition.
- A condition (even though it may have been present prior to the start of the trial) detected after the completion of the microdiscectomy or administration of the TFESI).
- Continuous persistent disease or symptoms present at baseline that worsens following the TFESI or microdiscectomy.
- Laboratory abnormalities that require clinical intervention or further investigation (unless they are associated with an already reported clinical event or as part of routine follow-up).
- Abnormalities in physiological testing or physical examination that require further investigation or clinical intervention.
- Injury or accidents that are not expected but are related to the microdiscectomy or TFESI.

[figure not shown]
SAEs, SARs/SUSARs and RUSAEs should be reported to the CTRC within 24 hours of the local site becoming aware of the event. The minimum information (see Section 10.7) required for each report should be completed by the investigator. The investigator should sign the causality of the event. Any additional information should be sent within 5 days if the reaction has not resolved at the time of reporting.

AEs related to the steroid and/or anaesthetic administered during the TFESI are defined as Adverse Reactions (ARs). If assessed as a Suspected Unexpected Serious Adverse Reaction (SUSAR) by the CI the event will be reported to the MHRA and REC by the CTRC.

AEs related to the microdiscectomy are defined as related Adverse Events (AEs). If assessed as a Related Unexpected Serious Adverse Event (RUSAE) by the CI the event will be reported to the REC by the CTRC.

Figure 1 shows the process that sites should follow when reporting adverse events:

